## Organ

Patients having lesions in more than one organ will not be included in the analyses by organ. In addition, only the following organs (Breast, Liver, Kidney, Pancreas, Prostate and those with more than 10% of patients for at least one reader) will be kept in the analysis.

## Descriptive statistics:

The 3 co-primary criteria will be summarized by contrast agent groups, MRI modalities (pre and paired) and organs using FAS1 and FAS2. Analysis using FAS 1 will show only co-primary criteria when gadopiclenol is administered.

Model:

In addition to the primary analyses, sensitivity analyses of the superiority analysis (on the FAS1) and of the non-inferiority analysis (on the FAS2) will be conducted using the same linear model with organ as additional factors.

The model syntax will be as follows for the sensitivity analysis of the superiority:

```
proc mixed data = XXX method = REML;
```

class subject MRI organ;

model eval = MRI organ MRI\*organ;

repeated MRI / subject=subject / type = cs;

lsmeans MRI MRI\* organ / pdiff = controlu('PRE') tdiff cl alpha = 0.025;

estimate "PAIRED - PRE" MRI\* organ 1 -1 ...../cl;

run; .

The model syntax will be as follows for the sensitivity analysis of the non inferiority:

```
proc mixed data = XXX method = REML;
```

class subject GBCA organ period;

model eval = GBCA organ period GBCA\*organ;

repeated GBCA / subject=subject / type = cs;

lsmeans GBCA GBCA\*organ / pdiff = control('gadobutrol') tdiff cl alpha = 0.025;

estimate "gadopiclenol - "gadobutrol" GBCA\*organ 1 -1 ..../cl;

run; .

The robustness of MRI modality or GBCA effect across different organs will be discussed with following information:

- Descriptive summary statistics for each organ
- Organ effect and organ\*MRI modality/GBCA interactions tests. These tests are used as exploratory indexes meaning that conclusions of these tests are just used as a support for discussion. Absence of statistical significance should not be taken to imply consistency. Absence of statistical significance in an interaction test, or only directional consistency, would not be sufficiently sensitive filters to detect differences of potential interest.
- MRI modality/GBCA effect estimations for each organ with the associated 95% two-sided CI. Overlapping of all organs CI estimates with the confidence interval for the overall effect will be checked by graphical visualization of the organs with a Forest plot for organ of the LS Means difference.

All these analyses will be performed for the co-primary criteria and statistical tests will be of help to “flag” potential problems, but descriptive assessments and clinical considerations need to be combined to evaluate potential signals.

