## Primary criteria 2: Lesion visualization criteria for gadopiclenol compared to gadobutrol (off-site read)

The same 3 co-primary criteria of lesion visualization: border delineation, internal morphology and degree of contrast enhancement, will be assessed on the images acquired during the MRI performed with gadopiclenol and those performed with gadobutrol.

The IBR will record each of the 3 co-primary criteria for up to 3 most representative lesions, on Paired images performed with gadopiclenol and Paired images performed with gadobutrol using a 4-point scale. Definitions of each co-primary criteria and score calculation are provided in primary criteria 1 description.

For each reader, only matching lesion on paired images between gadopiclenol and gadobutrol will be considered for the evaluation of the primary criteria 2.

For each reader, if the MR images are not assessable or if no matching lesion on Paired images between gadopiclenol and gadobutrol is identified, then the patient will not be included in the evaluation of primary criteria 2.

The mean score for each co-primary criterion of the lesion visualization will range from 1 to 4.

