**Body region**

Descriptive statistics:

The 3 co-primary criteria will be summarized by contrast agent groups, MRI modalities (pre and paired) and body regions using FAS1 and FAS2. Analysis using FAS 1 will show only co-primary criteria when gadopiclenol is administered.

Model:

In addition to the primary analyses, sensitivity analyses of the superiority analysis (on the FAS1) and of the non-inferiority analysis (on the FAS2) will be conducted using the same linear model with body region as additional factors.

The model syntax will be as follows for the sensitivity analysis of the superiority:

```
proc mixed data = XXX method = REML;
  class subject MRI body;
  model eval = MRI body MRI*body;
  repeated MRI / subject=subject / type = cs;
  lsmeans MRI body MRI*body / pdiff = controlu('PRE') tdiff cl alpha = 0.025;
  estimate "PAIRED - PRE" MRI*body 1 -1 ..../cl;
run; .
```

The model syntax will be as follows for the sensitivity analysis of the non inferiority:

```
proc mixed data = XXX method = REML;
  class subject GBCA body period;
  model eval = GBCA body period GBCA *body;
  repeated GBCA / subject=subject / type = cs;
  lsmeans GBCA body GBCA*body / pdiff = controlu('gadobutrol') tdiff cl alpha = 0.025;
  estimate "gadopiclenol - "gadobutrol" GBCA*body 1 -1 ..../cl;
run; .
```

The robustness of MRI modality or GBCA effect across different body regions will be discussed with following information:

- Descriptive summary statistics for each body region
- Body region effect and body region \*MRI modality/GBCA interactions tests. These tests are used as exploratory indexes meaning that conclusions of these tests are just used as a support for discussion. Absence of statistical significance should not be taken to imply consistency. Absence of statistical significance in an interaction test, or only directional consistency, would not be sufficiently sensitive filters to detect differences of potential interest.
- Effect estimations for each body region with the associated 95% two-sided CI. Overlapping of all body regions CI estimates with the confidence interval for the overall effect will be checked.
- Graphical visualization of the Body regions with a Forest plot for each body region of the LS Means difference and also the LS Means Ratio.

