**Percentage Enhancement of lesions (E%)**

E% is calculated from the Signal Intensity (SI) measurement of maximum 3 most representative lesions by the 3 independent off-site readers. The mean of E% will be calculated by patient using only matching lesions between GBCA

For each reader, E% will be tabulated by contrast agent groups using FAS 2. Differences between contrast agents will be tested using a Student's t-test. The models will include the contrast agent group and the period. The parameters of the general linear models with repeated measures will be estimated using the SAS® procedure Mixed. The difference between contrast agent groups in mean score and associated 95% two-sided CI will be computed.

The SAS® procedure used for the analysis will be the following:

```
proc mixed data = XXX method = REML;
  class subject GBCA period;
  model eval = GBCA period;
  repeated GBCA/subject= subject / type = cs;
  lsmeans GBCA / pdiff = control('gadobutrol') tdiff cl alpha = 0.025;
  /* The following code is needed as previous statement lsmeans does not provide the upper limit of CI */
```

CONFIDENTIAL	STATISTICAL ANALYSIS PLAN PHASE III TRIAL GDX-44-011 VERSION NO. 2.0      DATED 25 JANUARY 2021	████████ Page 39 / 57
--------------	---	--------------------------

lsmeans GBCA;  
estimate "gadopiclenol - gadobutrol" GBCA 1 -1 /cl;  
run; .

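### The organ program for gadopiclenol versus gadobutrol prints limits at both 97.5% and 95% without naming the reported source, and the organ exclusion rule does not say which lesions count

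*SAP*

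**What the plan says.** SAP 5.6.2, Examinations of subgroups, Organ, sets out the intended result: "MRI modality/GBCA effect estimations for each organ with the associated 95% two-sided CI". Overlap of these intervals with the overall interval is then to be judged by "graphical visualization of the organs with a Forest plot for organ of the LS Means difference".

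The program printed there for gadopiclenol versus gadobutrol has two lines that yield limits:
- LSMEANS, with "pdiff = control('gadobutrol') tdiff cl alpha = 0.025".
- ESTIMATE on GBCA*organ, with `/cl` and no alpha. Its coefficients are only sketched, ending in dots.

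The sibling programs are coded differently. The body-region program has "pdiff = controlu('gadobutrol') tdiff cl alpha = 0.025", and the demographic and magnetic-field program uses the same option. The organ program for Paired versus Pre has "pdiff = controlu('PRE') tdiff cl alpha = 0.025".

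The E% and LBR programs, later in 5.6.2, repeat the coding of the organ agent comparison. They follow it with this comment: "The following code is needed as previous statement lsmeans does not provide the upper limit of CI".

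On who is analysed, the Organ subsection says: "Patients having lesions in more than one organ will not be included in the analyses by organ". SAP section 4 contains the same rule. The score is defined more narrowly. Under primary criteria 2 in SAP 2.2.1, "only matching lesion on paired images between gadopiclenol and gadobutrol will be considered", up to three lesions per patient.

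**The concern.** With `controlu` (one-sided), alpha = 0.025 is coherent: the single lower limit coincides with the lower limit of a two-sided 95% interval. With `control` (two-sided), the same alpha gives a complete interval at 97.5%. In the sibling programs the missing upper limit prevents anyone from plotting the LSMEANS interval by mistake. Here a full interval at the wrong level is available. The organ intervals serve to check overlap with the overall effect, and wider bars make overlap easier, so a mistaken choice of source would lean towards a conclusion of consistency.

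The exclusion rule raises a different question. If any recorded lesion counts, a patient whose matching lesions are all in the liver leaves the organ analysis because one agent also showed an unmatched lesion in a kidney. Inclusion would then depend partly on what each agent detects, and small organ groups would lose usable patients.

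**Working it through.** **Inputs.**
- Stated level: two-sided 95% (SAP 5.6.2, Organ).
- Options and alphas: the programs in SAP 5.6.2.
- SD of the agent difference: 1.75, the planning value. The phase IIb basis gives 0.7 to 1.15 (SAP 3.3, primary objective 2).
- Organ group sizes: not given, so n = 10, 25 and 50 are assumptions. The protocol (section 3.1) sets enrolment minima of 25 and 50 for body regions, but none for organs.

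**Step 1. Level of each line.** A two-sided interval at alpha uses the quantile at 1 − alpha/2. A one-sided limit uses the quantile at 1 − alpha.

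| Line | Alpha | Sides | Critical z | Agrees with the stated 95%? |
|---|---|---|---|---|
| ESTIMATE `/cl`, organ | 0.05 (default) | 2 | 1.960 | yes |
| LSMEANS `controlu`, sibling programs | 0.025 | 1 | 1.960 | yes, for the lower limit |
| LSMEANS `control`, organ agent program | 0.025 | 2 | 2.241 | no, 97.5% |

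The stated figure is thus reproduced by the ESTIMATE line and not by the LSMEANS line.

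**Step 2. Size of the difference.** In large samples 2.241/1.960 = 1.144, or 14.4% wider. With t quantiles on n − 1 degrees of freedom, and half-width = t × SD/√n:

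| n (assumed) | Ratio | SD | 95% half-width | 97.5% half-width |
|---|---|---|---|---|
| 10 | 1.187 | 1.75 | 1.252 | 1.486 |
| 25 | 1.159 | 1.75 | 0.722 | 0.837 |
| 25 | 1.159 | 0.7 | 0.289 | 0.335 |
| 50 | 1.151 | 1.75 | 0.497 | 0.572 |

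The organ model pools organs, so its error degrees of freedom should exceed n − 1 for a single organ. The ratio would then lie nearer to 1.145, its value at 199 degrees of freedom.

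**Step 3. What the LSMEANS line estimates.** For GBCA*organ, `control('gadobutrol')` names an agent but no organ, so it does not clearly define a within-organ difference. The ESTIMATE line is the natural source, but as printed it lists only interaction coefficients. The treatment-plan program in 5.6.2 shows the full form: its within-category contrasts carry GBCA coefficients as well as interaction coefficients.

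**Step 4. The exclusion rule beside the score.**
- The score uses matching lesions only (SAP 2.2.1).
- The Location subsection of 5.6.2 assigns organs from the three most representative lesions, by agent and modality, with no matching condition.
- Elsewhere the SAP says when only matching lesions count (E%, LBR) or when unmatched ones are kept (lesion-level analysis, number of lesions). The organ rule says neither, and does not say whether it applies per reader.

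If a share f of an organ group is lost, the interval widens by 1/√(1 − f). For assumed f of 5%, 10%, 20% and 30%, that is 2.6%, 5.4%, 11.8% and 19.5%.

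**The case against.** The strongest reply is that the SAP already takes its intervals from ESTIMATE. In the primary superiority program of 5.6.1, comments assign the one-sided p-value to the LSMEANS `pdiff` line and the confidence interval to the lines that follow. The non-inferiority program has a similar comment, and the E% and LBR programs carry theirs right after the very coding in question. A plot of LS-means differences names a quantity, not a SAS statement. The body-region plot also needs two-sided intervals, which its one-sided LSMEANS line cannot supply. This stands. A reader might infer that the organ intervals are too wide. The documents do not support that, because the ESTIMATE line in the same program gives 95%. What remains is that the Organ subsection names no source and its ESTIMATE line is incomplete.

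On the exclusion, a reader might infer that the plan does drop patients because of unscored lesions. The text does not say so; it is silent on which lesions count. A rule is also needed, because a mean over scored lesions in two organs cannot be assigned to one. Nor does losing patients make an interval too wide for its stated level. It costs precision, and possibly comparability.

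The lesion-level analysis by organ, which keeps matching and unmatched lesions (Tables 14.2.2.14 and 14.2.2.15), partly covers the gap because it does not need one organ per patient. It answers a lesion-level question and leaves the patient-level rule undefined.

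**Conclusion.** The point holds as a coding inconsistency plus an ambiguity. The LSMEANS limits of the organ agent comparison are 97.5% where the text states 95%: about 14% wider in large samples, and 15% to 19% wider for n from 50 down to 10 if the degrees of freedom are n − 1. Reported intervals would be affected only if they were taken from that line, which the SAP neither directs nor rules out.

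The organ exclusion can, as worded, remove patients whose scored lesions lie in one organ. Its frequency, and any effect on the organ estimates, cannot be derived from the documents; the percentages for lost precision rest on assumed shares.

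The consequences are minor. The organ models are sensitivity analyses on FAS2, their interaction tests are called exploratory, and no margin is applied to organ limits. The primary non-inferiority test on PPS2 is untouched.

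**What to change.** - **Level.** In the organ agent program, use `controlu` with alpha = 0.025, as in the body-region and demographic programs, or `control` with alpha = 0.05.
- **Source.** State that the organ tables and forest plot come from ESTIMATE at 95%, and write out the within-organ contrast with both GBCA and GBCA*organ coefficients. Do not take them from the LSMEANS line, even after correction, because it names no organ level.
- **E% and LBR.** Correct the same pairing there. Keeping `control` and setting alpha = 0.05 preserves a two-sided test; the comment about a missing upper limit can then go.
- **Exclusion.** In SAP section 4 and the Organ subsection, define organ assignment and the multi-organ exclusion by the matching lesions that enter the patient's mean score, separately for each reader and comparison. Patients whose scored lesions span two organs would still be left out.

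The cost is one option in three programs, one written-out contrast and two or three sentences. No data are added, and the primary analysis does not change.

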## Intra-reader variability

Intra-reader variability will be analyzed in a subgroup of 10% of patients randomly selected for whom the off-site readers have re-read the images.

Intra-reader variability will be presented using data from gadopiclenol period on FAS1 on the one hand and using paired images from gadopiclenol and gadobutrol on FAS2 on the other hand.

Intra-reader variability will be studied by a Bland-Altman graph:

- Average of 1st and 2nd reading on X axis.
- Difference 2nd reading - 1st reading on Y axis.
- Horizontal lines at Mean, Mean + 1.96SD and Mean - 1.96SD, where Mean and SD are the mean and the SD of the difference of 1st and 2nd readings

One scatter plot per reader will be presented.

CONFIDENTIAL	STATISTICAL ANALYSIS PLAN PHASE III TRIAL GDX-44-011 VERSION NO. 2.0      DATED 25 JANUARY 2021	████████ Page 32 / 57
--------------	---	--------------------------

Descriptive statistics and the Intra-Class Correlation (ICC) will also be provided. It will be based on a one-way random effect model without observed effect:

$$Y_{ijk} = \mu + \alpha_i + \varepsilon_{ijk}$$

with  $\alpha_i \sim N(0, \sigma_\alpha^2)$  and  $\varepsilon_{ijk} \sim N(0, \sigma_\varepsilon^2)$  and  $\varepsilon_{ijk}$  is independent of  $\alpha_i$ .

$$ICC = \sigma_\alpha^2 / (\sigma_\alpha^2 + \sigma_\varepsilon^2)$$

which is estimated by

$$(MS_\alpha - MS_\varepsilon) / (MS_\alpha + MS_\varepsilon)$$

where  $MS_\alpha$  and  $MS_\varepsilon$  are the mean sums of squares from the one-way ANalysis Of VAriance (ANOVA) model for between and within subjects, respectively.

SAS® procedure used for the analyses of this secondary efficacy criterion will be the following for each off-site reader:

```
ods output OverallANOVA =icc0;
proc glm data=intra;
  class subject MRI modality reading;
  model BV = subject MRI modality reading;
run;
data ICC;
  retain sb sw;
  set icc0 end=last;
  if source='Model' then sb=ms;
  if source='Error' then sw=ms;
  if last then do;
    ICC=round((sb-sw)/(sb+sw), 0.01);
    output;
  end;
run;
```

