## 1.2. Trial design

The trial has a prospective, multi-center, randomized, double-blind, controlled and cross-over design.

The Investigational Medicinal Products (IMPs) used during the trial are gadopiclenol and gadobutrol. Patients will perform a screening visit (V1) to confirm trial eligibility, then will be randomized in the trial to determine the order of IMP injection. The randomization scheme will allocate patients in a 1:1 ratio to the two series, gadopiclenol-gadobutrol or gadobutrol-gadopiclenol. Each of the 2 MRI visits (V2 and V4) will be followed by a safety visit (V3 and V5) performed 1 day after the MRI visit.

Images will be evaluated by prospective evaluation of the blinded images in a centralized and blinded manner. The blinded image evaluations (off-site read) will be performed by 3 independent blinded radiologists for the reading of random images and by 3 additional independent blinded radiologists for the global pairs assessment.

As different body regions are included in the study, readers with different expertise were needed for the reading of study images. Hence, according to the different anatomic locations, a pool of 18 readers are selected and qualified for the entire study images reads:

- 6 readers for Head and Neck (H&N): 3 readers for global pairs assessments, 3 readers for all other assessments
- 6 readers Thorax (including breast), Abdomen (including liver, pancreas and kidney), Pelvis (including uterus, ovary and prostate) put together and labelled as Body
- 6 readers Musculoskeletal (including extremities) (MSK)

Within each of the 3 groups, 3 readers are allocated for global pairs assessments, 3 other readers for all other assessments (such as lesion visualisation parameters). Each group of readers will only read images as labelled by specific anatomic locations (H&N, Body and MSK).

As statistical analysis will be performed on the whole set of patients, 1 reader from each expertise domain are put together (1 reader H&N + 1 reader Body + 1 reader MSK), 3 times. So, each reader presented in the report is a combination of 3 readers.

For almost all analyses including the 2 primary analyses, readers are put together based on the numbering (reader 1, reader 2 and reader 3) allocated by the imaging CRO in charge of the reading at the beginning of the trial before the start of the reading.

	Body	MSK	H&N
Reader 1= B1+MSK1+ H&N1	reader B1	reader MSK1	reader H&N1
Reader 2= B2+MSK2+ H&N2	reader B2	reader MSK2	reader H&N2

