For each reader, only matching lesions between Paired images with gadopiclenol and Pre contrast images will be considered for the evaluation of the primary criteria 1.

For each reader, if the MR images are not assessable or if no matching lesion between Paired images with gadopiclenol and Pre contrast images is identified, then the patient will not be included in the evaluation of primary criteria 1.

The mean score for each co-primary criterion of the lesion visualization will range from 1 to 4.

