#### Inter-reader variability

Inter-reader variability will be evaluated on the whole set of study patients, since each case was read by 3 different readers.

Inter-reader variability will be presented using data from gadopiclenol period on FAS1 on the one hand and using paired images from gadopiclenol and gadobutrol on FAS2 on the other hand.

The same methodology as the one presented above for intra-off-site variability will be applied. One scatter plot for each of the 3 comparisons will be presented. The factor “reader” will be used instead of the factor “reading” in the model.

Presentation of patients and lesions.

Number of patients and lesions by contrast agents and MRI modalities for all efficacy datasets will be displayed using All Randomized Set.

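### The SAP's ICC program does not compute the one-way ICC it defines, and its formula is exact only for two records per patient

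*SAP*

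**What the plan says.** SAP section 5.6.2, Intra-reader variability, defines the ICC as patient variance over patient plus error variance, in a one-way random-effects model with no other term. It is estimated by (MSα − MSε)/(MSα + MSε), with both mean squares taken "from the one-way ANalysis Of VAriance (ANOVA) model for between and within subjects, respectively".

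The program in the same section fits "model BV = subject MRI modality reading" and reads the overall ANOVA table. It sets the between term with "if source='Model' then sb=ms", takes the within term from the Error row, and applies the same formula, "ICC=round((sb-sw)/(sb+sw), 0.01".

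The intra-reader data are the 10% of patients who are re-read: gadopiclenol-period images on FAS1, and paired images of both agents on FAS2. For Inter-reader variability, "The same methodology as the one presented above for intra-off-site variability will be applied", and "The factor “reader” will be used instead of the factor “reading” in the model".

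Two other provisions matter. Section 1.2 builds composite readers: "So, each reader presented in the report is a combination of 3 readers". Under section 2.2.1, a patient with no assessable images or no matching lesion for a given reader is dropped for that reader: "then the patient will not be included in the evaluation of primary criteria 1". The same holds for criteria 2. Section 5.2 admits a patient to FAS1 or FAS2 on a match for only one reader.

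**The concern.** There are two separate faults.

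- **Program against text.** The overall Model row pools patient, modality and reading (or reader). A systematic shift between image sets, readings or readers therefore enters the between-patient term and leaves the error. Two programmers, one following the prose and one the code, would report different ICCs.
- **Formula, in text and program alike.** It is the two-records form. The data have up to four records per patient (two image sets by two readings, or by one reader pair), or up to six if three readers enter together.

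The ICC is the single-number summary of reader consistency in a trial whose efficacy rests on subjective blinded scores. As coded, a larger contrast effect on FAS1 makes re-reading look more consistent. A given amount of reader disagreement may raise the ICC or not, depending on how it falls across anatomical groups.

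**Working it through.** The plan states no ICC value, so there is no figure to reproduce. The check compares the formula and the program with the SAP's own definition.

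**1. The formula.** Let va and ve be the patient and error variances and k the records per patient, with complete data and no shifts. Then E[MSα] = ve + k·va and E[MSε] = ve. In large samples the SAP form tends to k·va/(k·va + 2·ve). The form matching the definition is (MSα − MSε)/(MSα + (k−1)·MSε). For a true ICC of 0.50 (va = ve):

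- k = 2: 2/4 = 0.50
- k = 4: 4/6 = 0.67
- k = 6: 6/8 = 0.75

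**2. Intra-reader, FAS1.**

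- From the documents: 10% of 300 gives n = 30; two image sets by two readings gives 120 records; pre-to-paired shifts d of 0.41 and 1.59 are the smallest and largest mean differences in the cited gadobutrol study (Protocol 11.2, SAP 3.3).
- Assumed: va = ve = 0.25 (SDs of 0.5), so the true ICC is 0.50.

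Expected sums of squares are 29 × (0.25 + 4 × 0.25) = 36.25 for patients, 30d² + 0.25 for image set and 0.25 for reading. The model has 29 + 1 + 1 = 31 df and the error mean square is 0.25. At d = 1.59, 30d² = 75.84.

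- Program: sb = (36.25 + 75.84 + 0.25 + 0.25)/31 = 3.63, so (3.63 − 0.25)/(3.63 + 0.25) = 0.87.
- Written estimator: MSα = 1.25 and MSε = (90 × 0.25 + 75.84)/90 = 1.09, so (1.25 − 1.09)/(1.25 + 1.09) = 0.07.

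Means over 2,000 simulated data sets:

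| Shift | Program | Written estimator | One-way, correct k |
|---|---|---|---|
| 0 | 0.64 | 0.65 | 0.49 |
| 0.41 | 0.68 | 0.59 | 0.43 |
| 1.59 | 0.87 | 0.05 | 0.03 |

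With no shift, program and text agree and only the formula is at fault. As the shift grows they move apart. Correcting k alone does not rescue the pooled one-way model. With no patient variance at all (va = 0, ve = 0.5) the program still returns 0.71 at d = 1.59.

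**3. Inter-reader, FAS2, border delineation.**

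- From the documents: Phase IIb reader means 3.37, 1.97 and 3.72 (SAP 3.3). Their mean is 3.02, the deviations are 0.35, −1.05 and 0.70, and the sum of squared deviations is 1.715.
- Assumed: n = 200, all three readers together (k = 6), va = ve = 0.25, offsets common to all patients, and the modality term indexing the two paired image sets.

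Patient sum of squares: 199 × (0.25 + 6 × 0.25) = 348.25. Reader: 200 × 2 × 1.715 + 0.5 = 686.5. Image set: 0.25. Model df: 199 + 2 + 1 = 202.

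- Program: sb = 1035/202 = 5.12, so (5.12 − 0.25)/(5.12 + 0.25) = 0.91.
- Written: MSα = 1.75 and MSε = (1000 × 0.25 + 686)/1000 = 0.936, so 0.814/2.686 = 0.30.
- One-way with k = 6: 0.814/(1.75 + 5 × 0.936) = 0.13.

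Using the Phase IIb SDs and an assumed within-patient correlation of 0.25 to 0.50 instead, simulation gives 0.88 to 0.92 for the program, −0.09 to 0.17 for the written estimator, and −0.21 to −0.12 for a one-way ICC on each image set.

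**4. Composite readers.** Each analysed reader is three radiologists, so offsets need not be common. Suppose the same offsets rotate over the three groups. With a 60/20/20 split, a composite reader's mean offset is 0.6 − 0.2 = 0.4 of the original; with 80/10/10 it is 0.7; with equal thirds it is 0. The remainder falls into the error. The simulated program values, under the same SDs and correlations, become 0.22 to 0.39, 0.59 to 0.69, and −0.10 to 0.17. In the last case the program adds nothing to the written estimator. The splits are assumptions; the protocol gives only regional minimum numbers.

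**The case against.** **Weight.** The ICC is an add-on. Protocol 11.3.6 and SAP 5.6.2 study variability by Bland-Altman graph and provide the ICC besides. Those graphs draw the mean difference, so they show directly the offset that the program misplaces. No threshold or decision hangs on the ICC. This stands, and it limits the consequence.

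**Evidence.** The variances, correlations, group splits and offset patterns are assumed. The Phase IIb offsets come from other readers in patients with brain lesions and are driven by one outlying reader. Scores run from 1 to 4, and rounding and bounding them lowers the common-offset range to 0.85 to 0.89. The Inter-reader section asks for a plot for each of three comparisons, which makes a pairwise ICC plausible. For readers 1 and 2 alone, with common offsets, the program gives 0.79 to 0.86. All this is fair. It changes the size, not the algebra or the mismatch.

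**Where the fault lies.** Taking the pre-to-paired shift out of the error is sensible when measuring re-read consistency; the fault is adding it to the between term. At the smallest documented shift that adds only 0.68 − 0.64 = 0.04, and most of the rise from 0.50 comes from the formula. This also stands.

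**Benchmark.** The program can fall below the ICC for a single image set. With patient, patient-by-image and residual SDs of 0.3, 0.5 and 0.3 it gives 0.55 to 0.60 against 0.78. But on the SAP's pooled definition with k = 4 and no shift, MSα = 0.09 + 2 × 0.25 + 4 × 0.09 = 0.95 and MSε = 0.257. The ICC is then (0.95 − 0.257)/(0.95 + 3 × 0.257) = 0.40, and the program is still too high. The downward case therefore holds only against a per-image ICC.

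**Conclusion.** The concern holds. The program does not implement the one-way ICC defined in the same section, and the formula in both text and program is exact only for two records per patient. Neither point needs an assumption about the data.

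The formula alone turns 0.50 into 0.67 or 0.75 (large sample, complete data, no shift). The program's further departure grows with the systematic shift: small at 0.41, large at 1.59. Between readers its direction is conditional: strong inflation when offsets are shared by all patients, little or none when they differ by anatomical group. Sizes beyond the formula rest on normal scores and the assumed variances, correlations and splits.

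The ICCs should be corrected before they are reported. The primary analyses, the two-of-three-readers rule and the Bland-Altman plots are unaffected.

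**What to change.** Correct both the written estimator and the program.

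- For each image set separately (gadopiclenol pre, gadopiclenol paired, gadobutrol paired), fit a patient-only random-effects model. Report patient variance over patient plus residual variance from REML components.
- Alternatively use (MSα − MSε)/(MSα + (k0−1)·MSε), with k0 = (N − Σni²/N)/(m − 1), where ni is the number of records for patient i, N their total and m the number of patients. A fixed k = 3 is not exact, because not every reader scores every patient. In a check with true ICC 0.50 and 80% or 67% of patients scored per reader, fixed k = 3 gave 0.45 or 0.41; k0 (2.42 or 2.08) and REML both gave 0.50.
- Keep reader and reading out of the between-patient term.
- State in the Inter-reader section whether the three readers are analysed jointly or in pairs.

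Keeping a pooled model, but using the patient-row mean square with (k−1) in the denominator, also removes the shift problem: about 0.49 at every shift when the truth is 0.50. However, it leaves systematic reader offsets out of the ICC altogether, which the SAP's one-way definition does not.

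The cost is a few lines of code, the written formula and one sentence. Reported agreement may be lower, and REML stops at 0 where the ANOVA form can go negative.
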